7.1 DEMOGRAPHIC AND OTHER BASELINE CHARACTERISTICS

Only descriptive statistics are planned for this section of the report.

7.2 CONCOMITANT DISEASES AND MEDICATION

Only descriptive statistics are planned for this section of the report.

Use of pulmonary medications during treatment period and testing will be summarised in the end-of-text tables in the Clinical Trial Report (CTR) and a subject data listing of all concomitant medications will be provided in Appendix 16.2.

A table of number (%) of patients with concomitant diagnoses by system organ class (SOC) and preferred term (PT) will be included along with a supporting subject data listing. Concomitant diagnoses will be coded with the most recent version of the Medical Dictionary for Regulatory Activities (MedDRA) in effect at database lock.

Descriptive statistics and frequency tables (%) will be presented for history of trial indication.

Frequency tables (%) will be presented for COPD background characteristics.

7.3 TREATMENT COMPLIANCE

Only descriptive statistics are planned for this section of the report. Only descriptive statistics, i.e. the number (%) and percent of patients with compliance in the range of 80% - 120% will be provided. (cf. [Section 5.4](#) for calculation of treatment compliance).

7.4 PRIMARY ENDPOINTS

For the primary analysis, a mixed effect model repeated measures (MMRM) is specified in the protocol. This model will include treatment and period as fixed effects, patient as a random effect and period baseline as well as patient baseline as covariates. Compound symmetry will be used as a covariance structure for within patient variation. The SAS procedure MIXED will be used involving the restricted maximum likelihood estimation and the Kenward-Roger approximation for denominator degrees of freedom. This approach is described in (3). Adjusted mean values as well as treatment contrasts will be presented together with the 95% confidence intervals (CI) and p-values.

[figure not shown]
7.5 SECONDARY ENDPOINTS

7.5.1 Key secondary endpoints

This section is not applicable as no key secondary endpoint has been specified in the protocol.

7.5.2 Other Secondary endpoints

The MMRM described for the primary endpoint will be performed for all secondary continuous endpoints. Adjusted mean values as well as treatment contrasts will be presented together with the 95% CIs and nominal p-values. All p-values will be considered as descriptive.

7.7 EXTENT OF EXPOSURE

Extent of exposure is calculated as drug stop date minus drug start date plus one day and treatment interruptions are not taken into account in the calculation.

Extent of exposure will be summarised using descriptive statistics for the total treatment exposure in days as well as tabulation of number of patients with total exposure fall into the following categories:

- 1 day
- 2 – 21 days
- 22 – 42 days
- 43 – 63 days
- 64 - 84 days
- >=85 days.

7.8 SAFETY ANALYSIS

All safety analyses will be performed on the treated set.

7.8.1 Adverse events

The analyses of adverse events will be descriptive in nature and will be based on BI guideline “Handling and summarisation of adverse event data for clinical trial reports and integrated summaries” [\(4\)](#). All analyses of AEs will be based on the number of patients with AEs (not the number of AEs). For this purpose, AE data will be combined in a 2-step procedure into AE records.

In a first step, AE occurrences, i.e. AE entries on the CRF, will be collapsed into AE episodes provided that all of the following applies:

- The same MedDRA lowest level term was reported for the occurrences
- The occurrences were time-overlapping or time-adjacent (time-adjacency of 2 occurrences is given if the second occurrence started on the same day or on the day after the end of the first occurrence)
- Treatment did not change between the onset of the occurrences OR treatment changed between the onset of the occurrences, but no deterioration was observed for the later occurrence

In a second step, AE episodes will be condensed into AE records provided that the episodes were reported with the same term on the respective MedDRA level and that the episodes are assigned to the same treatment. For further details on summarization of AE data, please refer to BI guideline 'Handling and summarization of adverse event data for clinical trial reports and integrated summaries' [\(4\)](#).

Analyses of adverse events are based on the concept of treatment emergent adverse events. This means that all adverse events occurring between first drug intake and 21 days after last drug intake are assigned to the respective analysing treatment. All adverse events occurring before first drug intake are assigned to "screening" and all adverse events occurring after last drug intake + 21 days up to and including trial completion date are assigned to "post-treatment". AEs more than 21 days after drug stop date for a period but before the start of the next period will be assigned to 'washout'. AEs starting after trial completing date are assigned to "post-study". Screening, post-treatment and post-study AEs are presented in subject data listings only.

An overall summary of adverse events will be presented. A detailed description of the assignment of AE's to treatment can be found in [Section 6.1](#).

The frequency of patients with adverse events will be summarised by treatment, primary system organ class and preferred term. Separate tables will be provided for patients with other significant adverse events according to ICH E3 [\(5\)](#), for patients with adverse events leading to treatment discontinuation, for patients with adverse events leading to death, for patients with investigator determined drug-related adverse events, and for patients with serious adverse events.

According to ICH E3 [\(5\)](#), AEs classified as 'other significant' include those non-serious and non-significant adverse events with
(i) 'action taken = discontinuation' or 'action taken = reduced', or
(ii) marked haematological and other lab abnormalities or that lead to significant concomitant therapy as identified by the Clinical Monitor/Investigator and confirmed at a BRPM.

The system organ classes will be sorted according to the standard sort order specified by EMEA, preferred terms will be sorted by frequency (within system organ class).

Standard AE analyses requested for public disclosure at CT.gov and European Union Drug Regulating Authorities Clinical Trials will also be provided in Section 16.1.9.2 of the CTR.

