Concomitant therapy		X	X	X	X	X	$X^3$	X
Medication wash-out		X	X	X	X	X	X	

Boehringer Ingelheim 15 APR 2016

BI Trial No.: 1237.28

c03207491-01 Trial Protocol Page 9 of 137

Proprietary confidential information © 2016 Boehringer Ingelheim International GmbH or one or more of its affiliated companies

		Screening				Treatment Period1		
Visit	0	1	2	3	4, 7	5, 8	6, 9 (V9- EOT)	10
Week of treatment	1	1	-	-	0	3	6	V9-EOT + 3 weeks
Day of treatment Time Window (days)	-	-21 to -14	-13 to -9	-8 to -1	1	22 +7	43 + 7	V9-EOT + 21 + 7
Rescue Medication Use		X	X	X	X	X	$X^3$	
Trial Medication Adherence 						X	$X^3$	
Telephone contacts 		X	X	X	X	X	X	
Trial medication termination							X  (call IRT at V9 only)	
Trial completion								X

- 1. Treatment Period: In this cross-over design, each treatment period (period 1, period 2) will follow the same flow chart:
  - procedures during visits 4 and 7 will be identical (except for inclusion/exclusion check, randomisation and BDI at V4 only)
  - procedures during visits 5 and 8 will be identical
  - procedures during visits 6 and 9 will be identical
- 2. Informed Consent: All patients must sign an informed consent consistent with ICH-GCP guidelines prior to participation in the trial, which includes medication washout and restrictions.
- 3. Procedures: To be completed at the end of each treatment period and / or by all patients who took at least one dose of trial medication including those who discontinue early. PFTs are to be performed if possible.
- 4. Pregnancy Testing: Women of child-bearing potential: serum pregnancy test at visit 1; urine pregnancy test at visits 4, 6, 7, 9, 10.
- 5. ECG: 12-lead ECG recording at screening (visit 1) and end of treatment periods (visits 6 and 9) to be measured pre-dose.
- 6. Body Plethysmography: Conducted prior to dosing with salbutamol for inclusion.
- 7. Device Training: The patient will be instructed in the use of the Respirat® inhaler, but the patient **should not** inhale from the placebo inhaler at these visits.
- 8. Rescue Medication: To be supplied to all patients starting at visit 0.
- 9. Trial Medication Collection: Last dose of trial medication for the respective treatment period will be the morning dose, taken in the clinic on Day 43. All medication is collected after this dosing.

Boehringer Ingelheim BI Trial No.: 1237.28

c03207491-01

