Combinations	ICS/LABA (bid) (* switch to ICS mono-product, at the same or equivalent dose, at least 48 hrs prior to V1)	Permitted 	NOT permitted*	NOT permitted	NOT permitted	Permitted
	ICS/LABA (qd) (*switch to ICS mono-product, at the same or equivalent dose, at least 1 wk prior to V1) (e.g. fluticasone +vilanterol)	Permitted	NOT permitted*	NOT permitted	NOT permitted	Permitted
	ICS/SABA  (* switch to ICS mono-product, at the same or equivalent dose, at least 8 hrs prior to V1)	Permitted 	NOT permitted*	NOT permitted	NOT permitted	Permitted
	short-acting anticholinergic/ SABA (* 8 hrs prior to V1)	Permitted 	NOT permitted*	NOT permitted	NOT permitted	Permitted

c03207491-01 Trial Protocol Page 46 of 137

Proprietary confidential information © 2016 Boehringer Ingelheim International GmbH or one or more of its affiliated companies

			Study Period			
Drug Class	Sub-class	Prior to study	Screening Period	Treatment Period	Wash-out Period	Follow up Period
	Long-acting anticholinergics/long- acting β-adrenergics²(e.g. glycopyrronium+indacaterol, umeclidinium+vilanterol)	Permitted (w.o. 1 week prior to V1)	NOT permitted (w.o. 3 wks prior to V4)	Study medication	NOT permitted	Permitted
Antibiotics	For respiratory infections The use of antibiotics is not restricted and may be prescribed as medically necessary for COPD exacerbation episodes and / or infections.	Permitted (w.o. 4 wks prior to V1)	Permitted (except antibiotics for prevention of exacerbation of COPD)		n of COPD)	
	Any other infections	Permitted (w.o. 4 wks prior to V1)	Permitted	Permitted	Permitted	Permitted
Miscellaneous	Other investigational drugs (* 1 mth or 6 half-lives (whichever is greater) prior to V1)	NOT permitted*	NOT permitted	NOT permitted	NOT permitted	NOT permitted
	Cromolyn sodium / nedocromil sodium 	Permitted	Permitted	Permitted	Permitted	Permitted
	Antihistamines (including nasal route), antileukotrienes 	Permitted	Permitted	Permitted	Permitted	Permitted
	Methylxanthines 	Permitted 	Permitted 	Permitted 	Permitted 	Permitted 
	Mucolytics (not containing bronchodilators; stabilized 4 wks prior to V1)	Permitted	Permitted	Permitted	Permitted	Permitted
	Mucolytics containing bronchodilators	NOT permitted 	NOT permitted	NOT permitted	NOT permitted	NOT permitted

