#### 4.2.2.1 Restrictions for PFT and shuttle tests

- At least an 8-hour washout of short-acting beta-adrenergic bronchodilators.
- At least an 8-hour washout of short-acting anticholinergic bronchodilators prior to visits 1, 2, 3 and 4 (Not allowed during treatment periods but permitted during the wash-out period, with at least an 8-hour washout prior to V7).
- At least a 1-week washout of long-acting anticholinergic bronchodilators twice daily (bid) or once daily (qd) prior to visit 1 and a 3-week washout prior to visit 4. (Not allowed between visits 1 to 9).
- At least a 1-week washout of long-acting beta-adrenergic bronchodilators (qd) prior to visit 1 and a 3-week washout prior to visit 4 (Not allowed between visits 1 to 9).
- At least a 48-hour washout of long-acting beta-adrenergic bronchodilators (bid) prior to visit 1 (Not allowed between visits 1 to 9).
- The morning dose of inhaled steroids should not be taken in the 1-hour period prior to PFTs.
- Morning doses of study medication should not be taken prior to test-day pre-dose PFT.
- At least a 24-hour washout of short-acting (bid or more frequent administration) theophylline preparations.
- At least a 48-hour washout of long-acting (qd administration) theophylline preparation.

A patient visit may be re-scheduled twice due to lack of medication washout compliance. After this, a discussion with the Clinical Monitor should take place regarding the patient continuing in the trial

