# 7.3.3 Safety analyses

Adverse events will be coded using the Medical Dictionary for Regulatory Activities (MedDRA) coding dictionary. Standard BI summary tables and listings will be produced. All adverse events with an onset between start of treatment and end of the residual effect period (REP), a period of 21 days after the last dose of trial medication, will be assigned to the treatment period for evaluation.

All treated patients will be included in the safety analysis. In general, safety analyses will be descriptive in nature and will be based on BI standards. No hypothesis testing is planned.

Statistical analysis and reporting of adverse events will concentrate on treatment-emergent adverse events. To this end, all adverse events occurring between start of treatment and end of the residual effect period will be considered 'treatment-emergent'. The residual effect period is defined as 21 days after last dose of study medication (separately for each treatment period in the

BI Trial No.: 1237.28

c03207491-01 Trial Protocol Page 77 of 137

Proprietary confidential information © 2016 Boehringer Ingelheim International GmbH or one or more of its affiliated companies

crossover). Adverse events that start before first drug intake and deteriorate under treatment will also be considered as 'treatment-emergent'.

Frequency, severity, and causal relationship of adverse events will be tabulated by system organ class and preferred term after coding according to the current version of MedDRA.

Blood pressure and pulse rate measured in conjunction with PFT testing will be presented for each treatment using descriptive statistics.

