6. GENERAL ANALYSIS DEFINITIONS

6.1 TREATMENTS

The doses to be administered are described in Section 4 of the CTP.

This is a crossover trial consisting of a 3 to 4-week run-in period followed by two six-week treatment periods and a three-week post-treatment period. The day after the follow-up visit will be considered the start of the post-study period in case there are any subsequent AE data we become aware of. There will be 3-week washout between treatment periods.

For the main safety analysis, data occurring during the treatment periods and within 21 days of stop of study drug for the period will be assigned to the respective treatment for that period. Data occurring before the first drug intake date is assigned to “screening”. If the next treatment period starts within 21 days of the end of the last period, data after the start of treatment for the next period will be assigned to the treatment for that period. Data more than 21 days after drug stop date for a period but before the start of the next period will be assigned to washout. Data more than 21 days after the end of the last treatment period and up to and including the date of the study termination will be assigned to post-treatment. Data after study termination will be assigned to post-study.

Any cases of patient being treated with the wrong study medication will be identified and summarised as an important protocol violation (PV).

- If a patient was treated with a treatment sequence different from the randomised treatment sequence throughout the on-treatment period, i.e., a patient was treated with incorrect study medication during every treatment period, this patient will be included in the treated set and will be analysed as treated for both efficacy and safety analyses, including patient disposition. Such a case will be reported as an important PV and this patient will be excluded from the per-protocol set (PPS).

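### Adverse events in the 21 days after Visit 9 count under the last study treatment although open-label LABA is then permitted; a supplementary table with a shortened window is worth adding

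*SAP*

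**What the plan says.** **Attribution.** Under SAP 7.8.1, "all adverse events occurring between first drug intake and 21 days after last drug intake are assigned to the respective analysing treatment". SAP 6.1 says the same: "data occurring during the treatment periods and within 21 days of stop of study drug for the period will be assigned to the respective treatment". The rule comes from the protocol. Section 7.3.3 states "The residual effect period is defined as 21 days after last dose of study medication", applied separately to each crossover period, and section 5.3.7 treats events in that window as on treatment.

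**The one exception.** SAP 6.1 closes the window early only in this case: "If the next treatment period starts within 21 days of the end of the last period". Later data then go to the next period's treatment. Nothing closes the window when a non-study bronchodilator is started.

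**What patients may take.** In Table 4.2.2:1 the rows for inhaled LABA (twice and once daily), LAMA, ICS/LABA and LAMA/LABA read not permitted in the wash-out column and permitted in the follow-up column. Section 4.2.2.1 places the end of the restriction at Visit 9, for example: "At least a 48-hour washout of long-acting beta-adrenergic bronchodilators (bid) prior to visit 1 (Not allowed between visits 1 to 9".

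**Timing.** The flow chart notes say: "Last dose of trial medication for the respective treatment period will be the morning dose, taken in the clinic on Day 43". Follow-up then runs 21 days to Visit 10 (protocol 3.1), so the residual window after period 2 coincides with the follow-up period.

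**The concern.** One attribution rule covers two different exposures. After period 1 the 21 days are free of other long-acting bronchodilators. After period 2 they need not be. A patient in sequence AB (combination, then tiotropium) who resumes a LABA after Visit 9 has any event on that LABA reported under tiotropium. In sequence BA such events go to the combination, which already contains a LABA and a LAMA.

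The two treatments differ only by olodaterol, a LABA, and exclusion criterion 5 itself refers to the class side effects of β2-agonists. LABA-type events are therefore the ones a reader would most want kept apart by column. The overlap is also hard to see: SAP 7.2 summarises pulmonary medication for the treatment period and testing, so use in follow-up appears only in the listing of concomitant medications. Patients who stop study drug early and start other long-acting therapy within 21 days raise the same issue.

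**Working it through.** The plan gives no figure on this point, so there is none to reproduce. The check is a day count.

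**Inputs**
- 102 patients randomised 1:1 (protocol 4.1.4 and 7.7): 102 / 2 = 51 per sequence.
- 43 dosing days per period (flow chart notes).
- 21-day residual-effect period (protocol 7.3.3; SAP 6.1 and 7.8.1).
- Visit 7 planned on Day 64 from study start (SAP Table 6.7:1).
- Assumptions: everyone completes on schedule. The share f of patients who restart a LABA directly after Visit 9 is not in the documents and is varied.

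**Days attributed to tiotropium**
- Tiotropium first (BA): Day 1 to the day before Visit 7 = 63 days per patient.
- Tiotropium last (AB): 43 + 21 = 64 days per patient.
- Total: 51 × 63 + 51 × 64 = 3,213 + 3,264 = 6,477 patient-days. With a full 21 days after period 1 as well, 51 × 64 × 2 = 6,528.

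**Days on which open-label LABA is permitted**
- 51 × 21 = 1,071.
- 1,071 / 6,477 = 16.5% (or 1,071 / 6,528 = 16.4%).
- Within the last period alone: 21 / 64 = 32.8%.

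**LABA-exposed share of tiotropium-attributed time, f × 1,071 / 6,477**

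| f | share |
|---|---|
| 0 | 0% |
| 25% | 4.1% |
| 50% | 8.3% |
| 100% | 16.5% |

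**On the scale of the tables.** SAP 7.8.1 counts patients with events, not events. If q is the chance of a LABA-type event in 21 days of open-label use (also an assumption), the expected number of patients added to the tiotropium column is 51 × f × q:
- f = 25%, q = 2%: 51 × 0.25 × 0.02 = 0.26 patients (0.25 percentage points of 102).
- f = 50%, q = 5%: 51 × 0.50 × 0.05 = 1.28 patients (1.25 points).
- f = 100%, q = 10%: 51 × 1 × 0.10 = 5.1 patients (5.0 points).

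**Direction.** If restart is equally likely in both sequences, sequence BA adds the same expected number of events to the combination column. The difference in event counts does not move. Both columns rise, so the ratio moves towards 1. For patient counts this holds closely when events are uncommon, since a patient already counted is not counted again.

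**The case against.** **The window is the protocol's own definition.** This stands. The SAP follows protocol 5.3.7 and 7.3.3, and an inclusive 21-day rule is the cautious convention for safety. Starting another bronchodilator does not end the residual effect of the study drug.

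**A reader might infer that the main table should be cut at open-label restart.** The documents do not support that. The existing cut in SAP 6.1 moves events to another treatment's column. A cut at restart would move them to post-treatment, which SAP 7.8.1 shows in listings only. Serious events inside the residual-effect window would leave the summary tables. Restart may also follow deterioration, so the cut could remove events informatively, above all in patients who stopped early.

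**A reader might infer a large distortion.** Take an event caused only by LABA, at a constant daily rate, with immediate restart. The tiotropium count as a share of the combination count is then 1,071f / (102 × 43 + 1,071f) = 1,071f / (4,386 + 1,071f), or 10.9%, 16.3% and 19.6% for f = 50%, 80% and 100%. That is an artificial case. It counts events where the tables count patients, and the restart rate is unknown. It also supposes no such event on tiotropium alone, whereas salbutamol, also a β2-agonist, is available to everyone.

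**A reader might infer that the drug-related table is equally exposed.** It is less so. Protocol 5.3.6.1 asks the investigator to weigh concomitant medication when judging causality.

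What remains is the overlap itself, which no planned table lets the reader see or size.

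**Conclusion.** The overlap is real, but it is minor. In about 51 patients, events on open-label LABA after Visit 9 can be counted under tiotropium. The affected share of tiotropium-attributed time lies between 0% and 16.5%. The upper end needs every patient in sequence AB to complete and to restart a LABA at once, and the documents do not allow a narrower estimate.

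The consequence is overstated incidence in both columns and a ratio pulled towards 1 for LABA-type events. The expected absolute difference is not shifted, provided restart is equally common in both sequences. Safety is descriptive with no hypothesis test, and the primary analysis is unaffected. This is not an error by the SAP against the protocol, and it does not justify replacing the main table. It justifies a cheap supplementary display.

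**What to change.** Keep the protocol's 21-day residual-effect table as the main adverse event table. Add to SAP 7.8.1:

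- a supplementary table of treatment-emergent and serious adverse events, in which attribution ends at the earlier of 21 days after last study drug and the day before the first open-label long-acting bronchodilator (LABA, LAMA or a combination containing either);
- a flag in the listings on events that the shorter window excludes;
- the same handling for patients who stop study drug early.

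The start dates exist: concomitant therapy is reviewed at Visit 10 (protocol 6.2.3), and start dates are among the source data in protocol 8.3.1. The rule should be fixed before unblinding.

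The cost is one additional table and one programmed cut-off. The supplementary table has a shorter window for patients who resume long-acting therapy and should be read with that in mind. No event leaves the main tables, the protocol's residual-effect definition stays, and no rule on follow-up medication changes.
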